The study team for this K23 will be comprised of the Principal Investigator and applicant ([name]), Primary Mentor ([name]), and Co-Mentors (Drs. [name] and [name]). [name] will gain clinical trial research experience under the supervision of mentoring team. [name] will be primarily responsible for monitoring [name] implementation of all components of the study. The Co-Mentors will collaborate with and provide input to the PI in their given areas of expertise. The PI will be responsible for the day to day operations of the study including recruitment and data collection management and analysis. The administrative site will be at Emory University, Nell Hodgson Woodruff School of Nursing.

Study Team Training:

All team members have completed CITI training. Study-specific training for staff who will be obtaining data by interview.

Data Management and Monitoring:

Ongoing monitoring of this clinical feasibility trial will be conducted by the PI and mentor team throughout the study to ensure the trial is conducted according to the approved protocol. Drs. [name] and [name], both have experience with conducting clinical trials, will assist [name] in monitoring the study for safety and ensure that protection is assured throughout data collection. In addition, the Emory IRB will conduct regular reviews of study protocols, changes in study protocols, and adherence to protocols in the field. The PI is required to report any unexpected study-related adverse events to the Emory IRB and NIH. An independent safety monitor or a data and safety monitoring board will not be used.

Plans for Assuring Compliance with Requirements Regarding the Reporting of Adverse Events: The Principal Investigator is responsible for reporting serious adverse events to the Emory IRB and NIH within 48 hours of the occurrence.

A serious adverse event is defined as one that: is fatal or life-threatening (i.e., results in an immediate risk of death); requires or prolongs hospitalization; results in persistent or significant disability; is a birth defect; or is an important medical event that when based upon appropriate medical judgment, may jeopardize the participant, and may require medical or surgical intervention to prevent one of the outcomes listed above. Serious adverse events are not expected to occur during this study.

If there are instances of severe distress observed during the interviews, the we will provide the caregiver with a list of resources that the caregiver may use, such as counseling services or resources offered by Alzheimer's association. In emergent circumstances, the we will make a referral to the local emergency room.

Plans for Assuring Data Accuracy and Protocol Compliance: Under the direction of [name], all data will be managed in a secure fashion. All of the data will be kept on a secure server. In all of the data files, data will be coded by identification number only. Participants' names will be separated from the data and kept on a secure server or in a locked file cabinet. Access to the secure server and the file cabinet will be strictly controlled by the Principal Investigator.

Data Maintenance: We will use REDCAP to minimize data entry errors. All data entry screens are set up in REDCAP and, where possible, include data delimiters (i.e., skip patterns, valid range limits) to ensure correctness and minimize missing data.

Confidentiality:

Interactions with participants will take place in a private setting. All data will be coded by participants' identification numbers and kept in a locked file cabinet in the investigators' office. Consent forms will be stored separately from the data and will be limited to a few key personnel (PI and research team) involved in the study. When the interviews are transcribed, any identifiable information that was inadvertently mentioned (about anyone) will be removed from the transcript.

Benefits:

We are designing and testing the feasibility of an intervention and participants may not directly benefit. However, participants may derive some benefit from an increased awareness of meaningful activities for PLWD and their family caregivers. The potential risk for emotional distress is believed to be minimal and considered reasonable in view of the potential benefits for reducing stress and promoting well-being of dementia family caregivers of persons.

Compensation:

Phase 1 participants will receive \$25 honorarium upon completion of their semi-structured interview. Phase 2 caregiver participants will receive a \$25 honorarium for each baseline, endline, and qualitative interview completed for a total of \$75. In addition, they will also receive \$5 for each weekly diary entry completion, for an additional honorarium of \$60. Caregiver participants in Phase 2 possible compensation for total study participation is \$135.

Limitations, Challenges, and Strategies: This clinical trial feasibility study is an early stage of intervention development. A limitation of this study is related to not incorporating a control group into the design to avoid bias. Therefore, causal inferences regarding effects will not be made from the results of implementing the Faith-HAT. Accuracy of family caregiver report of behavior changes of the PLWD might be questionable due to recall bias. To counterbalance this challenge, caregiver participants will complete weekly entries about behavioral occurrences by their family member in their caregiver diaries. Asking participants to complete diaries of their weekly experiences allows for the gathering of their perceptions, thoughts, and feelings, as well as their family member's behavior and caregiving in context. However, using weekly caregiver diaries for data collection presents a challenge of maintaining caregiver motivation to ensure the diary entries are completed. Members of the research team will send weekly text message reminders, establish good working relationships with participants, and provide positive reinforcements to maintain motivation throughout study period. Recruiting AA participants into clinical research has been an ongoing challenge. If the aforementioned recruitment strategies do not obtain the desired sample, recruitment will be extended to advertising through social media, radio, senior centers, community newsletters, and other public venues.

Bibliography and References Cited

1. Pew Research Center. (2015). America's changing religious landscape. Retrieved from: <http://www.pewforum.org/2015/05/12/americas-changing-religious-landscape/>
2. Pew Research Center. (2014). U.S. public becoming less religious. Numbers, Facts, and Trends Shaping the World. <http://www.pewforum.org/2015/11/03/u-s-public-becoming-less-religious/>

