Aim 2. Test the feasibility and explore preliminary effectiveness of employing Faith-HAT. Our feasibility outcomes include success in recruitment, engagement, and retention in a purposive sample of 30 dyads. Our effectiveness outcomes include: caregiver-reported behavioral problems in PLWD; caregivers' self-reported psychological well-being (stress, burden, depression); and objective physiological measures of stress response (heart rate variability, skin conductance) to be measured at baseline and 12 weeks.

Aim 3. Construct a refined toolbox of meaningful faith-based home activities. Using integration and refinement of quantitative and qualitative data, results from Aim 2 will be matched, compared, and validated with the design team to refine the meaningful Faith-HAT for AA families living with moderate/severe dementia. The goal of this aim is to have materials ready for deployment for a fully powered clinical trial.

(C) Study Designs

Preliminary Studies: My previous qualitative work showed that families view participation in religious activities as a way to promote the physical and emotional health of AA older adults living with ADRD.^{17,41} The results of this study with 18 AA older adults living with ADRD and their family caregivers stressed the importance of religiosity to the well-being of PLWD.^{17,41} In fact, many PLWD were unable to physically attend church to worship as the disease progressed to the later stages, and families were left to come up with meaningful religious activities to do at home with their family member (i.e., singing gospel songs, praying, watching worship on the television).^{17,41} In my current work with the Atlanta-based Ministerial Alliance, we have found that families affected by ADRD do not attend church due to fear of embarrassment and uncertainty about the PLWD's behavior (Alzheimer's Association Research Diversity Grant 18-56229). These findings support the need for further exploration of religions' impact on AA families affected ADRD.

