or video-recorded sermons. We anticipate that families will have up 30 activities to choose from with the average activity length to be 10 minutes. The toolbox will be placed online. Participants will be able to access the toolbox via a tablet computer that will be provided to them. Before testing, member checks will occur with the design team and stakeholders for their feedback on fittingness and readiness for testing of Faith-HAT.

Aim 2. Test the feasibility and explore preliminary effectiveness of employing Faith-HAT. We will achieve this aim by conducting a feasibility clinical trial ($n = 30$). Our feasibility outcomes will include success in recruitment, engagement, and retention. Our effectiveness outcomes will include caregiver-reported perceived change in behavioral problems in PLWD as the primary outcome and caregivers' self-reported perceived psychological well-being (e.g., stress, burden, depression) and objectively measured physiological stress response (e.g., heart rate variability, skin conductance) as the secondary outcomes. We will use quantitative surveys, qualitative interview data, and caregiver diaries to assess psychological well-being and a wearable wristband to assess the physiological wellbeing.

Figure 3. Implementation Matrix

1-Design: A single arm pre-post design will be employed. Participants will be asked to take part in in-person survey and physiological baseline data collection, engage weekly in at least 3 activities from the Faith-HAT with person caring for living with ADRD for **6 weeks**, complete 12 weekly diary entries online through RedCap platform, and provide in-person survey and physiological endline data **immediately post-intervention and at 6-weeks post-intervention**. In addition to qualitative and quantitative measures, tracking of the enrollment and attrition rate will enable us to compute the “feasibility” of the program. Within the framework of a feasibility study,⁷³⁻⁷⁵ 12 weeks is a reasonable amount of time for the behavior toward the use of the Faith-HAT to be adopted and show meaningful effects.

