2. Participants: Despite AA family networks being complex and large involving blood and non-blood related individuals, there is often a family member that has the primary caring responsibility.⁷⁶ Therefore, a total of 30 dyads of AAs with moderate and severe ADRD and primary male or female caregivers will be recruited from the greater Atlanta area. Caregiver inclusion criteria: (a) at least 18 years of age; (b) reside with and care for (average of 4 hours/per day of unpaid assistance) for a family or friend experiencing signs and symptoms of moderate or severe ADRD as indicated through self-report or family caregiver report (c) able to read, speak, and understand English; (d) cognitively intact; (e) access to a wireless internet connection (wi-fi); and (f) access to a phone or mobile device that accepts text messages. PLWD inclusion criteria: (a) community-dwelling experiencing signs and symptoms of moderate or severe ADRD through self-report or family caregiver report; and (b) has a family caregiver that resides with them and is willing to participate; (c) no plan for institutionalization in the next month; (d) history of participating in private or public religious activities; and (e) understands English (toolbox activities will be produced in English). Family and self-reporting of the level of cognitive impairment will

be identified according to the signs and symptoms of moderate and severe ADRD associated with the Alzheimer's Association¹⁶ categorization of moderate/middle, and severe/late stages of dementia.

Caregiver exclusion criteria: does not have a history of participating in private or public religious activities; hostile to PLWD religious expression; and has active plans to move to another residence without family member with ADRD . PLWD exclusion criteria: has active plans to move from under care of primary caregiver; routinely attends church; hostile to religion; and unwilling to engage in Faith-HAT.

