3. Recruitment: A non-probability sampling strategy will be used to recruit a modest sample of 30 dyads of AA persons living with moderate and severe ADRD and their family caregivers to participate in Phase 2 of this clinical feasibility trial. The proposed sample size is justified through Browne's⁷⁷ general rule of using a minimum of 30 participants to have the capacity to estimate a parameter in a feasibility study. We will recruit participants over a 12- month period, with a target recruitment rate of 2-3 participants per month. We will recruit participants through churches in the South Fulton Ministerial Alliance and of the Emory ADRC Registry of Remembrance coalition (see letters of support). Announcements will also be placed in church bulletins of these churches. Church leaders and congregation members may also refer a caregiver that they know who may be interested in the study. If additional family caregivers are needed, we will use snowball recruitment by asking caregivers enrolled to refer other caregivers like them to participate.

Interested participants will be screened by the PI for eligibility via phone. If eligible, times will be scheduled to consent in person prior to beginning the study. Questions posed after explaining the project during eligibility determination and the consent process will be used to gauge participants' cognitive ability to take part in the project. The cognitive capacities of the caregiver and PLWD to provide consent will be assessed by using a five-item open-ended "Evaluation to Sign Consent" questionnaire with an established interrater reliability of 0.81.⁷⁸ Caregivers who are not able to correctly answer all items will be determined not to have the cognitive capacity to provide consent and participate. PLWD who are not able to correctly answer all items will also be deemed not to have cognitive capacity to provide consent; thus, they will provide assent and their primary caregiver will provide informed consent on their behalf.

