Aim 3. Construct a refined toolbox of meaningful faith-based home activities. No recruitment of participants and active data collection will occur for this aim. Qualitative and quantitative results from all data collection points from Aim 2 will be matched and compared to assist in refining the design of the Faith-HAT. The integration and interpretation of results through joint display and narrative discussion will be shared with the design team. Details of narrative discussion including caregiver discussion of activities to add, other ways to use the Faith-HAT, and circumstances under which engagement in Faith-HAT with the family member were optimal will be reviewed by the research and design team to develop a plan for program revision. Reasons for participant withdrawal and participant feedback on delivery characteristics will also be used to determine what components of the Faith-HAT will need to be revised. The research and design team will work together to produce a refined Faith-HAT program. Member checks of the refined toolbox with participants in Aims 1 and 2 will be conducted to improve the authenticity of the work and improve the accuracy, validity, and transferability of design readiness for deployment for a fully powered clinical trial.

Informed Consent Process:

Interested stakeholders and caregivers will be contacted by the PI or member of the research team to schedule a time to consent prior to data collection. Consents will be obtained at mutually agreed locations or via videoconference platform. Participants will be given the option to provide verbal consent after a discussion using a videoconference platform. After the videoconference discussion and verbatim review of verbal consent document, verbal informed consent will be obtained from the participant or legal representative and a copy of the consent will be mailed to them for their records.

Consents will be obtained at mutually agreed locations or provided by phone/videoconference. Consents will be obtained prior to data collection and the primary investigator will be responsible for obtaining consent.

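### Does a target of 2 to 3 recruits a month, with no attrition allowance, leave the study short of its 30 dyads?

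*Combined protocol and SAP*

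**What the plan says.** Under Aim 2, the participants section states that "a total of 30 dyads of AAs with moderate and severe ADRD and primary male or female caregivers will be recruited", and the recruitment section repeats the number as a plan to "recruit a modest sample of 30 dyads". The number is supported by a cited "general rule of using a minimum of 30 participants to have the capacity to estimate a parameter in a feasibility study". The accrual plan reads: "We will recruit participants over a 12- month period, with a target recruitment rate of 2-3 participants per month".

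The Aims section lists the feasibility outcomes as "success in recruitment, engagement, and retention in a purposive sample of 30 dyads". The design section adds that "tracking of the enrollment and attrition rate will enable us to compute" the feasibility of the programme. Aim 3 will use "Reasons for participant withdrawal and participant feedback on delivery characteristics" in revising the toolbox, so some withdrawal is foreseen. The text gives no attrition rate, no inflation for dropout and no target number of completers.

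Two provisions cover slow accrual. The recruitment section allows enrolled caregivers to refer others. The limitations section extends recruitment to social media, radio, senior centres and other public venues if the first strategies fall short. The quantitative analysis section says the study is not powered for formal hypothesis testing.

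**The concern.** Three things look wrong on a first reading.

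- **Rate.** A study that recruits 2 a month is inside its own target range, yet it closes the 12-month window with 24 dyads. Recruitment is a named feasibility outcome, so a rate that does not fill the study might be reported as meeting the target.
- **Unit.** The rate is in participants and the sample is in dyads. If participants meant individuals, 24 to 36 people would be only 12 to 18 dyads.
- **Attrition.** Thirty is presented as the minimum for estimating a parameter, but it is the number enrolled. If exactly 30 enrol and one dyad is lost, fewer than the minimum have endline data.

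At stake would be the meaning of two main feasibility results, recruitment and retention, and the claim that the sample is large enough to estimate anything.

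**Working it through.** **Inputs from the plan:** 30 dyads, 12 months, 2 to 3 per month, single arm, follow-up to 6 weeks after a 6-week intervention. **Assumed, because the plan gives none:** attrition of 10, 20 or 30%, and Poisson accrual at a constant rate.

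**1. Accrual (rate x 12, one participant per dyad).**
- 2 x 12 = 24, a shortfall of 6/30 = 20%. Reaching 30 would take 30/2 = 15 months.
- 2.5 x 12 = 30, the plan's own figure, at the midpoint of its range.
- 3 x 12 = 36. Reaching 30 would take 30/3 = 10 months.

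**2. Chance of at least 30 in 12 months.** With mean m = rate x 12, P(N >= 30) = 1 - sum over k = 0 to 29 of exp(-m) m^k / k!. This is 0.132 at m = 24, 0.524 at m = 30 and 0.862 at m = 36. The first value assumes that recruitment stays at 2 a month throughout and that neither slow-accrual provision is used or has any effect.

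**3. Unit.** Read as individuals, the top of the range is 36/2 = 18 dyads, so the plan could never reach 30. Read as one participant per dyad, the midpoint is exactly 30. The second reading also fits the rest of the text: the diary section calls the caregivers participants, and the recruitment section applies a minimum of 30 participants to 30 dyads.

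**4. Attrition with 30 enrolled.** Completers = 30 x (1 - d): 27 at 10%, 24 at 20%, 21 at 30%. Holding 30 completers would need 30/(1 - d), rounded up: 34, 38 and 43 dyads.

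**5. What depends on completers.**
- *Retention* has the enrolled dyads as denominator. If 24 of 30 stay, the estimate is 80% with an exact 95% interval of 61 to 92%. Dropout is what is being measured and does not reduce the 30.
- *Recruitment* is counted at enrolment and is unaffected.
- *Baseline standard deviation* of the behavioural-problems score uses all 30, since baseline data are taken at the enrolment visit. The 95% limits for an SD are the estimate times sqrt((n - 1)/chi-square quantile): 0.80 to 1.34 at n = 30. Even an SD taken from 24 dyads would have factors of 0.78 to 1.40.
- *Mean change from baseline* does lose precision. The 95% half-width in SD units of the change is t(0.975, n - 1)/sqrt(n): 0.37 at n = 30, 0.42 at n = 24 and 0.46 at n = 21.

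The planned mixed models for repeated measurements need not drop a dyad that misses one of the two post-intervention assessments. The completer counts in step 4 therefore lean towards the pessimistic side.

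**The case for a change.** The best case for a change is that this is a feasibility study, so its accrual benchmark bears on a main result. The text available shows no other numeric yardstick for recruitment, although the implementation matrix is a figure that is not reproduced. The lower end of the range is compatible with an unfilled study. The two slow-accrual provisions carry no numeric trigger and do not say that the 12 months may be extended. Stating the rate as 2.5 dyads a month, with an expected attrition, would cost nothing.

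The arithmetic in this stands, and so does the observation that recruitment success has no threshold. But the text never calls 2 a month a success; it gives a planning range. The Aims section ties recruitment to the sample of 30 dyads, and a reader would judge the result against that number. A later trial would be planned on the enrolment and attrition actually observed, which this study records, and not on the range written in advance. On attrition, whether the cited rule means 30 enrolled or 30 completing depends on a source outside the documents, so a breach of it cannot be shown here. What is left is a clarification the authors could make if they wished.

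**Conclusion.** No change follows. The range of 24 to 36 brackets the planned 30 and is centred on it; only the low end falls short, by 6 dyads, and the plan has further recruitment routes for that case. The mismatch between participants and dyads is a clerical slip with one reading that fits the rest of the plan. Leaving out an attrition allowance is a fair choice when retention is itself an outcome, no power or precision figure rests on 30, and the commitment is to dyads recruited.

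The cost is confined to the estimates of change from baseline: a half-width of 0.42 instead of 0.37 SD at an assumed 20% attrition, or 0.46 at 30%. The plan treats those analyses as preliminary. Restating the rate or the number would alter no enrolment, analysis or conclusion. This rests on reading one participant as one dyad and on attrition of no more than about 30%; the documents give no rate to check that against.

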Persons with dementia will be participating in Phase 1 and 2 of this research project. For Phase 1 and Phase 2, if the person living with dementia is unable to give a legally effective informed consent, verbal assent will be obtained with informed consent to be obtained from their legally authorized representative. If the family caregiver participating in the study is not the legally authorized representative, the PI will have to meet with the legally authorized representative for them to provide consent on behalf of the decisionally impaired adult.

For Phase 1 and 2, questions posed during the consent process will be used to gauge the person living with dementia cognitive ability to take part in the project and give consent. For participants with dementia providing verbal consent, questions will be posed during the videoconference discussion with their caregiver or legal representative present to gauge the person living with dementia cognitive ability to take part in the project and give consent. If there remain concern about their capabilities to consent, an "Evaluation to Sign an Informed Consent" will be completed by the primary investigator.

If the person living with dementia is determined unable to give a legally effective informed consent, verbal assent will be obtained with informed consent to be obtained from their legally authorized representative. Participant eligibility requires for caregivers to be able to read, speak, and understand English and for persons living with dementia to be able to speak and understand English. The investigator will orally review the consent form with them and answer any questions they may have. Potential participants will be asked to describe what their participation in the study will involve and what is meant by voluntary participation. Potential participants needing more time to decide whether to participate will be allowed more time as needed.

The following measures will be implemented to minimize the possibility of coercion or undue influence: explaining the (a) voluntary nature of participation; (b) any alternatives to participating; (c) ability to withdraw at any time; and (d) fact

that the decision whether or not to participate will have no impact on the availability of care through Emory Healthcare System.

All aspects of the study will be communicated to the participant or legally authorized representative.

Organizational Structure:

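### Recruitment lets the primary caregiver consent for a person without capacity, while the consent section requires the legally authorized representative; the two rules diverge when these are different people

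*Combined protocol and SAP*

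**What the plan says.** Under Aim 2, item 3 (Recruitment), capacity is assessed with a five-item open-ended questionnaire, and the threshold is a full score: "PLWD who are not able to correctly answer all items will also be deemed not to have cognitive capacity to provide consent". In that case, "they will provide assent and their primary caregiver will provide informed consent on their behalf". The sentence does not ask whether the caregiver holds legal authority, and it does not refer to any other section.

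The Informed Consent Process section covers Phases 1 and 2. When a person living with dementia cannot give legally effective consent, "verbal assent will be obtained with informed consent to be obtained from their legally authorized representative". It then takes up the case in which caregiver and representative differ, and its instruction there is that "the PI will have to meet with the legally authorized representative for them to provide consent on behalf of the decisionally impaired adult". Its paragraph on videoconference consent is consistent with this: "verbal informed consent will be obtained from the participant or legal representative".

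Under Aim 2, item 2 (Participants), the person with dementia qualifies if he or she "has a family caregiver that resides with them and is willing to participate", among other criteria. The caregiver criteria allow care "for a family or friend experiencing signs and symptoms of moderate or severe ADRD". Neither list mentions legal authority. Item 5 (Study visits) has the principal investigator arrange a visit with the participating caregiver that covers consent, enrolment, training and baseline data. It does not name a representative.

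**The concern.** Two sections give different rules for one event: a person with dementia is found unable to consent and someone else must do so. One names the caregiver, the other the legally authorized representative. If these are different people, Recruitment accepts a consent that the consent section treats as insufficient.

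What is at stake is first the protection of adults with impaired decision-making. The trial enrols only people with moderate or severe dementia, and one wrong answer on the questionnaire is enough to require surrogate consent, so surrogate consent is likely to be common. The secondary issue is data. The primary effectiveness outcome is caregiver-reported behavioral problems in the person with dementia, so a question over that person's consent bears on that outcome.

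**Working it through.** The plan gives no figure on this point, and the contradiction depends on none. The check is a comparison of the sections.

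**Step 1. The rules side by side, for a person who lacks capacity.**

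| Situation | Recruitment | Informed Consent Process | Same result? |
|---|---|---|---|
| Caregiver is the representative | Caregiver consents | Representative, i.e. the caregiver, consents | Yes |
| Caregiver is not the representative | Caregiver consents | Investigator meets the representative, who consents | No |

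The conflict is confined to the second row.

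**Step 2. Can the second row occur?** Yes. The consent section provides for it, and no criterion under Participants excludes it. The possibility of a friend as caregiver adds some plausibility but does not decide the matter. The criteria for the person with dementia ask for a family caregiver, a relative need not be the representative, and a friend might be. The documents do not define who qualifies as representative.

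**Step 3. Would the planned workflow catch it?** Not by itself. Recruitment describes a phone screen for eligibility followed by a scheduled consent, and legal authority is not among the eligibility criteria. Study visits then puts consent and baseline into one visit with the caregiver. The prompt to find the representative appears only in the consent section.

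**Step 4. How many dyads?** A dyad is affected only if three things coincide:

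expected number = 30 × P(no capacity) × P(caregiver is not the representative, given no capacity) × P(consent section not followed, given both)

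The documents supply only the 30. With each probability free between 0 and 1, the result runs from 30 × 0 = 0 to 30 × 1 = 30. One dyad is 1/30 = 3.3% of the sample. Multiplying 30 by an assumed share of caregivers who are not representatives would set the first and third probabilities to 1, so it would give a ceiling under that assumption and not an estimate.

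**Step 5. A related mismatch.** Recruitment uses the questionnaire to assess capacity without condition. The consent section has the investigator complete the evaluation only if concern remains after questions during the consent discussion. The trigger for surrogate consent therefore also differs between the two sections.

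**The case against.** The strongest reply is that the right rule is already in the plan. The dedicated consent section covers both phases, states the representative rule more than once, and deals with the very case in which caregiver and representative differ. The Recruitment sentence can be read as shorthand for the usual case. The principal investigator screens participants, is responsible for consent and is the person who must meet the representative, so nothing suggests that separate staff work from Recruitment alone. A faulty enrolment requires the consent section to be overlooked.

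Most of this stands, and it lowers the risk considerably. It does not remove the conflict. Neither section refers to the other or says which governs, and the visit description follows the caregiver-only route.

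A reader might infer more than the documents support, in four ways:

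- **That the diverging case is certain to arise.** The text shows only that it may.
- **That a particular number of dyads is at risk.** None of the three probabilities in the working is given.
- **That affected dyads would be lost from the analysis.** No rule for dropping data is stated. Burden, stress, depression, the diaries and the wristband recordings come from the caregiver, who consents separately. The most that is in question is the person with dementia's participation and the caregiver's reports of that person's behavior.
- **That such consent would be legally invalid.** That depends on law outside the documents. They support only the statement that it would not be the consent the protocol's own section requires.

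**Conclusion.** The contradiction is real and should be corrected. For a person without capacity whose caregiver is not the legally authorized representative, Recruitment and the Informed Consent Process section give incompatible instructions. Eligibility does not rule the case out, and the visit description has no step that would detect it. Following Recruitment and Study visits alone could enrol a person without the consent that the protocol requires.

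This is an inconsistency between sections and not evidence that consent will fail. Its size in dyads cannot be estimated. The conclusion rests on the text alone, with validity judged by the protocol's own standard. The statement that surrogate consent will be common is an inference from the disease stage and the full-score threshold, since the documents give no rate.

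**What to change.** Reword the Recruitment sentence to match the consent section: a person without capacity gives assent and the legally authorized representative gives informed consent, with the caregiver doing so only if he or she is that representative. Carry the same condition into the Study visits description, so that consent and baseline do not go ahead with a caregiver who lacks that status. Confirm representative status before the baseline visit. One question at the existing phone screen would be enough, though another method would also serve. In the same edit, state once when the capacity questionnaire is used, since the two sections differ on that as well.

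The cost is a few sentences and one check at screening. Some dyads will need an extra contact with the representative, which the consent section already foresees. Sample size, outcomes and analysis are unchanged.
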